5.11.2.2.3 Supportive analysis

The same analysis proposed for estimands #1 will be repeated on PPS.

5.11.2.2.4 Additional non-parametric analysis

A non-parametric analysis will be performed considering Estimand #1 as described in Table 1. The Hodges-Lehmann estimate of the difference between IFB-088 and placebo along with 95%CI and Wilcoxon p-value will be provided.

5.11.2.2.5 Descriptive analysis

In addition, a descriptive summary of observed ALSFRS-R Score values at baseline, Month 3 and Month 6 as well as their change from baseline to month 3 and to month 6 will also be provided.

STATISTICAL ANALYSIS PLAN		
InFlectis BioScience	Sponsor:	InFlectis BioScience
	Protocol Number:	P288ALS
VERSION 1.0 NOV 12, 2024		

5.11.2.2.6 Subgroup Analysis

Subgroup analyses will be performed considering Estimand #1 only, based on an ANCOVA model including terms for treatment, subgroup, treatment by subgroup interaction and baseline ALSFRS-R score. Treatment effect with 95% CI and p-value will be estimated by subgroup within this model. P-value of the test for interaction will also be provided.

Subgroups are as follows.

- Baseline NFL (neurofilament light chain): \leq median vs $>$ median
- Country: France vs Italy
- Sex: Man vs Woman
- ALSFRS-R progression rate (point/month) (from symptoms onset to screening visit): \leq median vs $>$ median
- Time from onset date of first ALS symptoms to screening: \leq median vs $>$ median

A forest plot will display the treatment effects by subgroup with 95% CI and p-values and treatment by subgroup interaction p-value

5.11.2.3 Change in ALSFRS-R total score from baseline to Month 3 (V3)

The analysis will be performed considering estimand #1 at month 3 on FAS .

The same analysis proposed for the change in ALSFRS-R score from baseline to Month 6 will be proposed at month 3.

Missing ALSFRS-R score at Month 3 will be imputed with the same method considered for estimand #1 definition at month 6, i.e. as follows:

Missing data will be handled depending on the type of the intercurrent event (i.e.).

- Missing data due to deaths occurring prior to Month 3:
 - a) due to disease progression, the ALSFRS-R score at month 3 will be imputed by the worst value (i.e. 0)
 - b) other reason (sudden death included): the missing ALSFRS-R score at month 3 will be imputed by linear extrapolation based on the predicted value in the linear regression model including terms for intercept and baseline ALSFRS-R score estimated within the treatment group to which the patient is randomized. Imputed values will be rounded to the nearest integer.

Calendar time of V3 will be considered as 90 days.

- Missing data due to drop-outs or withdrawal occurring prior to Month 3 will be imputed with the same approach used for handling missing data due to deaths for other reasons (i.e. other than disease progression).

STATISTICAL ANALYSIS PLAN		
InFlectis BioScience	Sponsor:	InFlectis BioScience
	Protocol Number:	P288ALS
VERSION 1.0 NOV 12, 2024		

Note: Imputed values will be rounded to the nearest integer. Imputed value higher than 48 will be replaced by 48 and imputed value lower than 0 will be replaced by 0.

The additional non-parametric analysis will also be performed considering Estimand #1 only.

5.11.2.4 Change in ALSFRS-R Subscores from baseline to Month 6 (V4)

The ALSFRS-R consists of 3 domains (bulbar, motor and respiratory)

The 3 subscores will be considered as follows:

- Bulbar subscore: sum of items 1-3
- Motor subcore : sum of items 4-9
- Respiratory subcore: sum of items 10-12

The analysis of each subscore will be performed considering estimand #1 at month 6 on the FAS. Missing subscore will be imputed with the same method considered for estimand #1 definition of the ALSFRS-R total score at month 6, i.e., as follows:

Missing data will be handled depending on the type of the intercurrent event (i.e.).

- Missing data due to deaths:
 - a) due to disease progression, the ALSFRS-R subscore at month 6 will be imputed by the worst value (i.e. 0)
 - b) other reason (sudden death included):
 - if the ALSFRS-R subscore is not missing at Month 3, the ALSFRS-R subscore at month 6 will be imputed by linear extrapolation given baseline and Month 3 ALSFRS-R score available values. Note: in the linear extrapolation at month 6, the timepoint of ALSFRS assessment considered at V3 will be the exact calendar date of V3 assessment. Calendar time of V4 will be considered as 180 days. Imputed values will be rounded to the nearest integer.
 - if the ALSFRS-R subscore is missing at Month3, the ALSFRS-R subscore at month 6 will be imputed by linear extrapolation based on the predicted value in the linear regression model including terms for intercept and baseline ALSFRS-R subscore estimated within the treatment group to which the patient is randomized. Imputed values will be rounded to the nearest integer.
- Missing data due to drop-outs or withdrawal will be imputed with the same approach used for handling missing data due to deaths for other reasons (i.e. other than disease progression). Imputed values will be rounded to the nearest integer.

Note: Imputed value lower than 0 will be replaced by 0.

STATISTICAL ANALYSIS PLAN		
InFlectis BioScience	Sponsor:	InFlectis BioScience
	Protocol Number:	P288ALS
VERSION 1.0 NOV 12, 2024		

For bulbar subscore: imputed value higher than 12 will be replaced by 12.

For motor subscore: imputed value higher than 24 will be replaced by 24.

For respiratory subscore: imputed value higher than 12 will be replaced by 12.

The analysis of each subscore will be performed in an ANCOVA model including terms for treatment and baseline ALSFRS-R subscore in FAS. The additional non-parametric analysis will also be performed in FAS.

5.11.2.4.1 Subgroup Analysis

Subgroup analyses of each ALSFRS-R subscore will be performed considering Estimand #1 only, based on an ANCOVA model including terms for treatment, subgroup, treatment by subgroup interaction and baseline ALSFRS-R subscore in FAS. Treatment effect with 95% CI and p-value will be estimated by subgroup within this model. P-value of the test for interaction will also be provided.

Subgroups are as follows.

- Baseline NFL (neurofilament light chain): \leq median vs $>$ median
- Country: France vs Italy
- Sex: Man vs Woman
- ALSFRS-R progression rate (point/month) (from symptoms onset to screening visit): \leq median vs $>$ median
- Time from onset date of first ALS symptoms to screening: \leq median vs $>$ median

A forest plot will display the treatment effects by subgroup with 95% CI p-values and treatment by subgroup interaction p-value.

5.11.3 Analysis of change in ALS-Milano-Torino staging system (MITOS)

5.11.3.1 Expressions

This parameter will be expressed in terms of:

- Value at baseline and at each planned visit (V3, and V4).
- Change from baseline to each post baseline visit.
- Change from V3 to V4.

STATISTICAL ANALYSIS PLAN		
InFlectis BioScience	Sponsor:	InFlectis BioScience
	Protocol Number:	P288ALS
VERSION 1.0 NOV 12, 2024		

5.11.3.2 Change in MITOS Stage from baseline to Month 6 (V4)

5.11.3.2.1 Primary analysis

The primary analysis of the Change in MITOS stage from baseline to Month 6 will be conducted on the FAS as described in Table 2.

The Change in MITOS stage will be analyzed as a binary endpoint defined as the progression (versus non-progression) of the MITOS stage to a higher stage at 6 months compared to baseline. Hence, subjects who did not progress to a higher stage at 6 months compared to baseline stage are “non-progressors”. “Non-progressors” will be modelled in the analysis.

Missing data at month 6 whichever reason (death or drop-out prior to month 6) will be imputed as progressors (i.e. with a higher stage at month 6 compared to baseline stage).

The difference in rates of “non-progressors” at month 6 between IFB-088 vs placebo along with 95% CIs and p-value will be estimated according to the binomial exact method.

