8. STATISTICS

8.1 STATISTICAL AND ANALYTICAL METHODS

8.1.1 General statistical considerations

Statistical analyses will be performed by the sponsor or under the supervision of the sponsor and further detailed in the SAP, which will be finalised prior to the unblinding of data and database lock.

In general, summary tabulations will be presented by treatment arm and will display the number of observations, mean, standard deviation (SD), median, Q1, Q3 quartiles, minimum, and maximum for continuous variables, and the number and percent per category for categorical data.

Patient disposition

An accounting of study patients by disposition will be tabulated and the number of patients in each analysis set will be summarised. Patients who discontinue study treatment and patients who withdraw from the study, with associated reason(s), will be summarised. A summary of protocol deviations by treatment arm and the corresponding listing by patient will be generated.

Nominal alpha level of significance

Unless otherwise noted, as the trial is a safety trial and an estimation efficacy study and not powered for efficacy endpoints, all tests performed on efficacy assessments will be conducted at a 1-sided nominal alpha level of 0.10 and confidence intervals (CIs) will be calculated at 80%, 2-sided 95% confidence intervals will also be provided.

Missing data handling

As a general rule, missing data will not be replaced. Sensitivity analyses based on multiple imputation will be proposed and further detailed in the SAP.

Multiplicity

As it is mainly an estimation trial, there is no adjustment for multiplicity.

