- Worsening (i.e. progression to a higher stage at 6 months compared to the baseline stage defined by ALS-MITOS score): the proportion of progressors will be compared between both treatment groups. The difference in binomial proportions will be estimated along with an exact 95% CI. A sensitivity Bayesian analysis using the historical placebo data from the ProMISe study [26] will be also performed and further detailed in the SAP. Progressors will also be analysed in a logistic regression model adjusting for treatment and additional relevant covariates (specified in the SAP). The treatment effect will be estimated in terms of an odds ratio associated with the 95% CI and p-value and also in terms of a difference in progression rates with its 95% CI using the method proposed by Ge and al. [45].
- Change in King's College score: the endpoint will be analysed with an approach similar to the analysis of ALS-MITOS score.

Analyses of the changes in efficacy endpoints from baseline to month 3 (as inferential analysis) and from month 3 to month 6 (as descriptive analysis) will be also proposed and further detailed in the SAP.

- Respiratory function: changes from baseline to 3 months and from baseline to 6 months will be analysed. Analyses will be further detailed in the SAP.
- Bioelectrical analysis: changes from baseline to 3 months and from baseline to 6 months will be analysed for the planned following parameters: phase angle, Z200/Z5 impedance ratio, skeletal muscle mass, dry mass, and dry mass without fat. Analyses will be further detailed in the SAP.

PK Analysis

Individual plasma concentrations of IFB-088 and IFB-139 (i.e. IFB-088 metabolite) with corresponding nominal sampling times, will be tabulated for each subject and scheduled sampling time, together with descriptive statistics. Mean plasma IFB-088 concentrations profiles by cohort will be presented over time graphically, using blood sampling time (x axis) and concentrations (y axis) on both linear and semi-log scales.

Derived and observed PK parameters will be evaluated by noncompartmental analysis. The following parameters will be listed and summarised by cohort, as appropriate:

- AUC, ng.h/mL,
- C_{max}, ng/mL, with associated T_{max}, h,

- Terminal or apparent terminal $t_{1/2}$, h,
- Apparent systemic clearance (Cl/F, L/h) and apparent volume of distribution (Vd/F, L) at steady state, where F is the overall oral bioavailability of IFB-088.

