4 RANDOMIZATION

All participants were centrally randomised in a 2:1 allocation ratio to receive either IFB-088 + riluzole or placebo + riluzole, respectively. No stratification factor was considered. The randomisation was performed through an interactive web response system (IWRS) integrated into the eCRF. Before the study is initiated, the log in information and directions for the IWRS was provided to each site. Once a set of medical characteristics is entered, the IWRS immediately assigned a patient to one of the 2 arms. After the randomisation visit, the investigator automatically received a confirmation by email with the treatment number allocated to the patient.

This is a double-blinded study. Neither participants, nor investigators, nor trial staff, nor the sponsor study team was aware of treatment assignments prior to the database lock at the conclusion of the study.

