5.11.1.1 Nominal alpha level of significance

As the trial is a safety trial and an estimation efficacy study and as it is not powered for efficacy endpoints, all tests performed on efficacy assessments were planned to be conducted at a 2-sided nominal alpha level of 0.20. 2- sided 95% confidence intervals will be provided.

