5.11.4.2 Change in King's College stage at Month 6 (V4)

5.11.4.2.1 Primary analysis

The primary analysis of the Change in KCL stage from baseline to Month 6 will be conducted on the FAS as described in Table 3Erreurs ! Source du renvoi introuvable.. The Change in KCL stage will be analyzed as a binary endpoint defined as the progression (versus non-progression) of the KCL stage to a higher stage at 6 months compared to baseline. Hence, subjects who did not progress to a higher stage at 6 months compared to baseline stage are “non-progressors”. “Non-progressors” will be modelled in the analysis.

Missing data at month 6 whichever reason (death or drop-out prior to month 6) will be imputed as progressors (i.e. with a higher stage at month 6 compared to baseline stage).

The difference in rates of “non-progressors” at month 6 between IFB-088 vs placebo along with 95% CIs and p-value will be estimated according to the binomial exact method.

The ratio of rates of “non-progressors” at month 6 between IFB-088 vs placebo along with 95% CIs and p-value will be estimated according to the binomial exact method.

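### The SAP drops, without declaring it, the protocol's covariate-adjusted analysis of MITOS and King's progression, and does not name the exact test that remains

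*SAP*

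**What the plan says.** **Protocol 8.1.5.2.** Two analyses of MITOS progression at 6 months are planned. The first is an unadjusted difference in proportions with an exact 95% CI. The second is additional: "Progressors will also be analysed in a logistic regression model adjusting for treatment and additional relevant covariates (specified in the SAP"). It is to yield an odds ratio with 95% CI and p-value, and also a "difference in progression rates with its 95% CI using the method proposed by Ge and al". The Synopsis has the same plan and adds the randomisation stage to the adjustment terms. King's is to follow a similar approach.

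**SAP Tables 2 and 3, 5.11.3.2.1 (MITOS) and 5.11.4.2.1 (King's).** Only the unadjusted comparison remains. For MITOS the difference in rates "between IFB-088 vs placebo along with 95% CIs and p-value will be estimated according to the binomial exact method". King's has the same for the difference and the ratio. No covariate is named and no regression model is described, although 5.11.4.2.1 still says "Non-progressors” will be modelled in the analysis" and 5.11.3.2.1 has matching text.

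**Level.** SAP 5.11.1.1: "all tests performed on efficacy assessments were planned to be conducted at a 2-sided nominal alpha level of 0.20". Protocol 8.1.1 has efficacy tests that "will be conducted at a 1-sided nominal alpha level of 0.10".

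**Allocation.** SAP Section 4: "All participants were centrally randomised in a 2:1 allocation ratio to receive either IFB-088 + riluzole or placebo + riluzole, respectively", with no stratification factor.

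**Declared changes.** SAP Section 7 lists the move from MMRM to ANCOVA, the new imputation for deaths and the deletion of the Bayesian analysis. Removal of the logistic model is not listed.

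**The concern.** The protocol left the choice of covariates to the SAP, and the SAP removed the model instead of filling it in. Three things follow.

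- Chance imbalance in baseline function between two small, unstratified arms is left uncorrected for the staging endpoints. The SAP does adjust for baseline in its models for ALSFRS-R total and subscores, NfL, TDP-43 and SVC, so these two endpoints are the exception.
- The dropped model was the only MITOS analysis to which the protocol explicitly attached a p-value. The test has moved to the crude comparison, and a reader of Section 7 would not know it.
- The remaining test is not identified. Exact tests for two small binomials differ materially in how much of the 0.20 level they use, so the plan does not yet fix the operating characteristics of the comparison.

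**Working it through.** **Inputs from the documents.** 50 randomised, 2:1, hence about 33 v 17; 42 evaluable, 28 v 14; two-sided 0.20 (SAP 5.11.1.1). A missing month-6 stage counts as progression, so drop-outs stay in the denominator and 33 v 17 is the relevant size. The plan's own sample-size figures reproduce: 1 - 0.95^28 = 76.2%; 1 - 0.90^28 = 94.8%; 42/0.85 = 49.4, rounded up to 50. The documents give no power, size or expected progression rate for MITOS or King's, so the rates below are assumptions.

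**Step 1. Size of the exact test.** For common rate p, size = sum over all (a, b) of Bin(a; 33, p) x Bin(b; 17, p) x 1{p-value(a, b) <= 0.20}.

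| Common rate | Fisher, two-sided | Unconditional exact (score-ordered) |
|---|---|---|
| 0.2 or 0.8 | 13.9% | 19.9% |
| 0.3 or 0.7 | 14.1% | 19.6% |
| 0.4 or 0.6 | 13.0% | 18.4% |
| 0.5 | 12.8% | 17.5% |
| 0.9 | 10.9% | 17.8% |

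At 28 v 14 and rates 0.2 to 0.8, Fisher's size is 14.0-16.5%. One-sided Fisher at the protocol's 0.10, at 33 v 17, has size 4.0-5.7%.

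**Step 2. Power, same enumeration with different rates, 33 v 17.**

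| Non-progression, placebo to active | Fisher | Unconditional exact | Loss (points) |
|---|---|---|---|
| 0.3 to 0.5 | 41.7% | 50.1% | 8.4 |
| 0.4 to 0.6 | 44.4% | 50.7% | 6.3 |
| 0.5 to 0.7 | 48.2% | 54.6% | 6.4 |
| 0.5 to 0.8 | 77.2% | 81.7% | 4.5 |
| 0.7 to 0.85 | 40.1% | 49.8% | 9.7 |

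Over the twelve pairs of rates tried, the loss is 4.5 to 9.7 points. At 28 v 14 it is 0 to 2.8 points.

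**Step 3. How much imbalance is left uncorrected.** Assume a baseline ALSFRS-R SD of 3 points. The standard error of the between-arm difference in baseline mean is 3 x sqrt(1/33 + 1/17) = 3 x 0.2985 = 0.90 points. At an assumed log-odds of 0.15, 0.30 or 0.45 per point, a one-standard-error imbalance shifts the log-odds by 0.13, 0.27 or 0.40. Near a 50% rate, multiplying by 0.25 gives at most about 3, 7 or 10 percentage points.

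**Step 4. What the covariate itself buys.** Simulation at 33 v 17, placebo non-progression about 50%, odds ratio 3, baseline SD 3, two-sided 0.20, 1,500 runs per setting:

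| Log-odds per point | Fisher | Firth, unadjusted | Firth, adjusted | Gain from covariate |
|---|---|---|---|---|
| 0.15 | 60.0% | 66.5% | 66.1% | -0.4 |
| 0.30 | 54.7% | 61.7% | 63.9% | +2.2 |
| 0.45 | 44.5% | 53.1% | 59.7% | +6.6 |

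A separate run of 2,500 per setting agrees. The unconditional exact test had 68 / 62 / 52% power and the adjusted Firth likelihood-ratio test 69 / 65 / 59%, a gain of 1 / 3 / 7 points. Adjusted Firth held its level at about 17-20%; unpenalised adjusted logistic regression ran at about 19-23%, hence the penalty.

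**Step 5. Precision.** The simulated SD of the estimated difference is 0.144 / 0.143 / 0.146 crude and 0.134 / 0.127 / 0.122 adjusted, 7 to 16% smaller. Part of this is Firth shrinkage: with no prognostic effect the SD already falls from 0.143 to 0.135, which is 5.6%.

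**The case against.** The unadjusted exact difference is the protocol's own first-listed analysis, so the SAP did not introduce it. Efficacy is secondary, explicitly unpowered and unadjusted for multiplicity, and the SAP's ALSFRS-R analysis already adjusts for baseline. A conservative test on a secondary endpoint is arguably the safer error. All of that stands, and it limits how serious the point is.

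A reader might infer something stronger: that by dropping the covariates the SAP committed itself to a test that rejects only 13% under no effect, and so gives up 5 to 12 points of power. The documents do not support this.

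- The SAP does not say Fisher. Fisher's test yields no CI for a rate difference, and an exact CI for a difference is usually unconditional. An unconditional test uses 17-20% of the nominal 20%.
- Most of such a gap comes from Fisher's conservatism, not from losing the covariate. An unadjusted Firth test recovers much of it (Step 4).
- The upper end needs a very strong covariate. Entry requires ALSFRS-R of at least 36, a span of at most 12 points; 0.45 per point implies an odds ratio of exp(5.4), about 221, across that span, and 0.30 implies about 37. No document gives either value.

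The prognostic link is also weaker for King's. MITOS is built from ALSFRS-R items, whereas King's rests on regions affected and the need for gastrostomy or ventilation. A patient with lower baseline function may already sit at a higher King's stage with less room to move, so even the direction is uncertain. Making the logistic model the sole 0.20-level test would go beyond the protocol, which described it as additional.

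**Conclusion.** The point holds as an undeclared omission with a cheap remedy. The protocol's adjusted logistic analysis and adjusted rate difference are missing for both staging endpoints, and Section 7 is incomplete without that entry.

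There are two effects, and they should be kept apart. Not naming the exact test leaves the size at 33 v 17 anywhere from about 13-14% (Fisher, common rates 0.2-0.8) to about 17-20% (unconditional exact), a difference of roughly 5 to 10 power points. Losing the covariate costs about 0 to 5-7 power points for MITOS under an assumed baseline SD of 3 and log-odds of 0.15-0.45 per point, and an uncertain amount for King's. The documents supply neither progression rates nor prognostic strength, so these are ranges under assumption. They do not show that the SAP's method as written has 13% size, or that the lost adjustment alone costs 5 to 12 points. The primary safety objective is unaffected. This should be fixed, but it does not threaten the trial's main conclusion.

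**What to change.** - **SAP 5.11.3.2.1 and 5.11.4.2.1:** reinstate the protocol's logistic regression beside the exact comparison, with treatment and baseline ALSFRS-R (continuous), a Firth penalty for sparse counts, the odds ratio with CI and p-value, and the adjusted difference by the Ge method. Say whether the Synopsis term for randomisation stage is kept. For King's, present the model as supportive.
- **Same sections and Tables 2 and 3:** name the exact test, preferably an unconditional exact test consistent with the exact CI for the difference, so that p-value and interval come from one procedure.
- **Section 7:** if the adjusted analysis is not restored, list its removal and give the reason.
- **Timing:** fix all of this before unblinding. A covariate named later, in a post-lock addendum, would be open to choice in the light of the results.

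The cost is SAP wording and a short program. No new data are needed, because baseline ALSFRS-R is scheduled for every patient. The downside is a one-covariate model in about 50 patients.

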5.11.3.2.2 Supportive analysis

The same analysis will be repeated on the PPS.

